### 8.2.11 Other Derived Variables

#### ECG Corrected QT Interval

Fridericia's corrected QT (QTcF):  $QT \text{ interval} / [(RR \text{ interval}/1000)^{1/3}]$ , where RR interval is in msec. If RR is missing, then the formula to use is:  $QT \text{ interval} / [(60/HR)^{1/3}]$ , where HR = heart rate in beats per minute.

#### Body Mass Index (BMI)

BMI will be calculated using the following formula:

$$BMI \text{ (kg/m}^2\text{)} = \text{Weight (kg)} / [\text{Height (cm)}/100]^2$$

using the height measured at Screening and the weight measured at Day 1 (if available). If weight at Day 1 is not available, the assessment at Screening will be used (if available). If neither is available, then BMI is missing.

#### Age

Age at informed consent will be calculated using the following formula:

$$\text{Age (years)} = \text{floor}(\text{intck('month', BirthDate, InformedConsentDate)} - \text{day(InformedConsentDate)} < \text{day(Birthdate)}) / 12$$

In addition, age at informed consent will be categorized as 18-65, >65-75, or >75.

#### Race

Idera Pharmaceuticals, Inc.  
 Statistical Analysis Plan  
 Protocol Number: 2125-MEL-301

---

For subgroup analyses, race will be categorized as white and non-white.

## Region

For subgroup analyses, region will be categorized as US and non-US.

### 8.3 SAFETY PARAMETER RANGES

#### 8.3.1 Laboratory Parameters

Reported laboratory values will be categorized using value ranges that reflect the severity grades in the National Cancer Institute Common Terminology Criteria for Adverse Events (NCI-CTCAE) v4.03 for the relevant laboratory parameters. See [Appendix Section 16.5](#).

Laboratory values will also be categorized relative to the normal range: a value that is outside the reference range is either high abnormal (value above the upper limit of the normal [ULN] reference range) or low abnormal (value below the lower limit of the normal [LLN] reference range).

Local laboratories were used in this study. Some of the local laboratories did not provide reference ranges for the corresponding results. For these cases, the reference ranges from the American College of Physicians will be used. Below is the link to these reference ranges: <https://annualmeeting.acponline.org/sites/default/files/shared/documents/for-meeting-attendees/normal-lab-values.pdf>

#### 8.3.2 ECG Parameters

To report QTcF values, categories referencing the grades in the NCI-CTCAE v4.03 will be used (see adverse event ‘Electrocardiogram QT corrected interval prolonged’). Additionally, the post-baseline increase in corrected QT values will be summarized using the ranges below.

ECG Parameter	Reporting Range	Unit
Absolute QTcF interval	$\geq 450$ to $< 481$ $\geq 481$ to $< 501$ (Grade 2) $\geq 501$	msec
Increase from baseline QTcF	Increase of $\geq 31$ to $\leq 60$ Increase of $> 60$	msec

The following criteria will be used to flag other clinically significant post-baseline ECG values:

Idera Pharmaceuticals, Inc.  
 Statistical Analysis Plan  
 Protocol Number: 2125-MEL-301

ECG Parameter	Out of Normal Ranges	Unit
PR interval	<110 (L) and >220 (H)	msec
QRS interval	<75 (L) and >110 (H)	msec

### 8.3.3 Vital Signs

The following criteria will be used to summarize heart rate shift tables:

Vital Sign Parameter	Reporting Range	Unit
Heart Rate	< 50 50 to 120 > 120	bpm

To summarize blood pressure, the below categories will be used to produce shift tables.

Vital Sign Parameter	Reporting Range	Unit
Systolic Blood Pressure	< 90 ≥90 to <120 ≥120 to <150 ≥150 to <180 ≥180	mmHg
Diastolic Blood Pressure	< 50 ≥50 to <70 ≥70 to <90 ≥90 to <110 ≥110	mmHg

To summarize temperature, categories below will be used to produce shift tables.

Vital Sign Parameter	Reporting Range	Unit
Temperature	≤35 > 35 to < 38 ≥38	Degrees Celsius

## 9 DEMOGRAPHICS, BASELINE DISEASE CHARACTERISTICS, AND SUBJECT DISPOSITION

Unless otherwise stated, all tables and listings in this section will be based on the ITT Analysis Set.

### 9.1 DISPOSITION OF SUBJECTS

The number and percentage of subjects in each analysis set will be summarized, as will subject status at the end of the study, comprising completed (death), ongoing, or withdrawn

Idera Pharmaceuticals, Inc.  
Statistical Analysis Plan  
Protocol Number: 2125-MEL-301

---

from the study, with reasons for study withdrawal; and study treatment status, comprising completed study treatment or prematurely discontinued study treatment, with reasons for premature discontinuation of study treatment. Duration of active follow-up, defined as the duration between the date of randomization and the date of last disease assessment, in months as well as duration of survival follow-up defined as the duration between the date of randomization and the date of last contact or death, in months will be summarized descriptively.

- Analysis Sets
- Subject Status
- Study Treatment Status
- Duration of Active Follow-up
- Duration of Survival Follow-up

Reasons for study withdrawal and study treatment discontinuation will be presented in the order they are displayed in the electronic Case Report Form (eCRF).

The following listings will be provided:

- Subject disposition
- Reasons for study withdrawal
- Reasons for study treatment discontinuation

This analysis will be repeated for FAS and Per Protocol Analysis Set for sensitivity analysis.

## **9.2 PROTOCOL DEVIATIONS**

Protocol deviations will be categorized as major or minor as defined in 2125-MEL-301 Protocol Deviation Plan. A subset of major protocol deviations will be further classified as exclusionary from the Per Protocol Analysis Set if they are considered having significant impact on the primary efficacy data. The following summary will be provided:

- Major protocol deviations by category

The following listings will be provided:

- All inclusion and exclusion criteria violations
- All protocol deviations including major designation and exclusionary classification from the Per Protocol Analysis Set

## **9.3 DEMOGRAPHIC AND BASELINE DISEASE CHARACTERISTICS**

The following summaries will be provided:

Idera Pharmaceuticals, Inc.  
Statistical Analysis Plan  
Protocol Number: 2125-MEL-301

---

- Demographic and baseline characteristics (age at consent, age categories [18-65, >65-75, >75], race, ethnicity, sex, country, region, height, weight, BMI, baseline lactate dehydrogenase [LDH], LDH categories [ $\leq$ ULN, >ULN], baseline neutrophil/lymphocyte ratio, and ratio categories [ $<2.5$ ,  $\geq 2.5$ ])
- Baseline disease characteristics (primary histology, stage, tumor PD-L1 immunohistochemistry result, elevated LDH, BRAF mutation status, and ECOG performance status at baseline)
- Prior systemic anticancer treatment history (all settings)
- Prior systemic anticancer treatment history (unresectable/metastatic disease setting only)

The following listings will be provided:

- Demographic characteristics
- Baseline disease characteristics (excluding ECOG performance status)
- Medical history
- Prior systemic anticancer treatment, including best response and reason for discontinuation if available
- Prior cancer-related surgeries
- Prior radiotherapy
- ECOG performance status

The demographic and baseline disease characteristics analyses will be repeated for FAS and Per Protocol Analysis Set for sensitivity analysis.

#### **9.4 STRATIFICATION FACTORS**

The number of subjects at each stratification factor level at randomization and from the clinical data will be summarized using frequencies and percentages and listed. The summary will be by marginal levels of duration of prior anti-PD-1 therapy ( $\geq 12$  weeks vs  $< 12$  weeks), metastasis stage (M1c vs other), and BRAF mutation status and prior targeted therapy (BRAF wild type [i.e., negative], BRAF mutation positive with prior targeted therapy, or BRAF mutation positive with no prior targeted therapy) as well as the 12 stratification cells. The listing will show the randomized and clinical data stratification levels for each subject.

The duration of anti-PD-1 therapy in weeks will be calculated using start and end dates reported on the Prior Systemic Anticancer Treatment page of the eCRF as (therapy end date – therapy start date + 1)/7 when a therapy is referred to as “PD-1 inhibitor”.

Metastasis stage will be identified from the Baseline Disease Characteristics page of the eCRF as M1c or Other (if not M1c).

Idera Pharmaceuticals, Inc.  
Statistical Analysis Plan  
Protocol Number: 2125-MEL-301

---

BRAF mutation status is reported on the Baseline Disease Characteristics page of the eCRF as negative or positive. Prior targeted therapy for BRAF mutation positive subjects will be identified as the treatment category of prior systemic anticancer therapy of BRAF inhibitor, MEK inhibitor, other targeted therapy, or any combination of these therapies for those subjects with “Positive” BRAF mutation.

[Section 8.2.10](#) describes how the stratification factors are combined. The combined stratification levels will be summarized showing the levels with metastasis stage (M1c or Other) and BRAF mutation status (BRAF wild type or BRAF mutation positive).

The following summaries will be provided:

- Stratification factor levels as randomized
- Stratification factor levels derived from the clinical data
- Stratification factor levels as combined

The following listing will be provided:

- Stratification factor levels

## 9.5 CONCOMITANT MEDICATIONS

Concomitant medications will be coded using the World Health Organization (WHO) Drug Dictionary Version B3 Sep 2020. A concomitant medication is defined as any drug or substance administered between the time of the first dose of study treatment and 30 days from the date of the last dose of study treatment, or taken to treat SAEs, irAEs, AEs of Grade 3 or above that occurred within 90 days of the last dose of study treatment, or taken to treat Grade 3 or above treatment-related AEs and SAEs that occurred during either the Active or Survival follow-up periods. This includes medications that were started prior to screening if their use continued during dosing. If the start date or end date of concomitant medication is partial, use the imputation rules defined in [Section 8.1.2](#) to impute the date and determine if the medication was concomitant.

In the summary of concomitant medications, each subject is counted once within each unique term. For example, if a subject takes Amoxicillin on two separate occasions, the subject is counted only once under the ingredient “Amoxicillin”.

The summary of concomitant medications using the Safety Set will show the number and percentage of subjects taking concomitant medications by therapeutic class and preferred term (PT). Anatomical Therapeutic Chemical (ATC) Level 4 will be used for the listing and summary.

Idera Pharmaceuticals, Inc.  
 Statistical Analysis Plan  
 Protocol Number: 2125-MEL-301

A similar summary will also be generated for concomitant medications that were used to treat immune-related adverse event as recorded on the Concomitant Medication eCRF page.

Another summary will be generated by category of concomitant immune-modulating medications that were used to treat irAEs. These medication categories include thyroid hormone replacement therapies, systemic steroids, and immune-suppressants. Thyroid hormone replacement therapies will be identified by WHO drug ATC prefix H03, systemic steroids by WHO drug ATC prefix H02, and immuno-suppressants by WHO drug ATC prefix L04. Any medications with one of these prefixes that were indicated on the Concomitant Medication eCRF page as being used to treat irAEs will be included in this summary by preferred term under the corresponding category.

Cancer treatments including, but not limited to, radiotherapy, anticancer treatment, and surgery that occurred after the start of study treatment and were received during the study will be summarized separately. If a subject received more than one type of cancer treatment, he/she will be counted under each of them in the summary. The best overall response from these cancer treatments and procedures will be included in the summary. Biopsies and other diagnostic procedures will not be considered as cancer treatment.

IMO-2125 is a cytokine modulator that may indirectly affect cytochrome P450 (CYP) production or activity, and subsequently affect the exposure to CYP substrates. Therefore, increased AEs or decreased efficacy may occur in patients concurrently administered CYP-sensitive substrates or substrates with a narrow therapeutic range. Any concomitant medications identified as CYP-sensitive substrates or substrates with a narrow therapeutic range will be summarized and listed including any AE(s) that started during the duration of the treatment. The medications of interest are as follows:

Drug Category	Preferred Term
Sensitive CYP3A4 substrates	budesonide, buspirone, eplerenone, eletriptan, felodipine, fluticasone, lovastatin, midazolam, saquinavir, sildenafil, simvastatin, triazolam, vardenafil
CYP3A4 substrates with a narrow therapeutic range	alfentanil, astemizole(a), cisapride(a), cyclosporine, diergotamine, ergotamine, fentanyl, pimozide, quinidine, sirolimus, tacrolimus, terfenadine(a)
Sensitive CYP1A2 substrates	duloxetine, alosetron
CYP1A2 substrates with a narrow therapeutic range	theophylline, tizanidine

Idera Pharmaceuticals, Inc.  
 Statistical Analysis Plan  
 Protocol Number: 2125-MEL-301

Drug Category	Preferred Term
Sensitive CYP2C8 substrates	repaglinide
CYP2C8 substrates with a narrow therapeutic range	paclitaxel
CYP2C9 substrates with a narrow therapeutic range	warfarin, phenytoin
Sensitive CYP2C19 substrates	omeprazole
CYP2C19 substrates with a narrow therapeutic range	s-mephenytoin
Sensitive CYP2D6 substrates	desipramine
CYP2D6 substrates with a narrow therapeutic range	thioridazine

The following summaries will be provided:

- Concomitant medications
- Concomitant medications for irAEs by category (thyroid hormone replacement medications, systemic steroids, immune-suppressants)
- Cancer treatments and surgeries after the start of study treatment
- Concomitant sensitive and narrow therapeutic range CYP substrates

The following listings will be provided:

- Prior and concomitant medications
- Cancer treatment after start of study treatment
- Sensitive and narrow therapeutic range CYP substrate - concomitant medications for subjects who used CYP substrates during the study
- Sensitive and narrow therapeutic range CYP substrate - treatment-emergent adverse events started during or after use of CYP substrates

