### **11.5 IMMUNE-RELATED ADVERSE EVENTS**

Immune-related AEs (irAEs) are side effects associated with the increased activity of the immune system by immunotherapy agents such as checkpoint inhibitors, which can affect multiple organs of the body including the skin, gastrointestinal tract, endocrine system, liver, lungs, nervous system, and musculoskeletal system.

The following list of AEs were provided in the protocol as a guide to the investigators to identify the immune-related AEs. Any AEs which have been associated with the use of immunotherapy agents were marked as immune-related in the CRF.

- Adrenal insufficiency
- Hypophysitis
- Hypopituitarism
- Hypothyroidism
- Hyperthyroidism
- Other endocrinopathies
- Colitis
- Enterocolitis
- Dermatitis
- Autoimmune dermatitis
- Guillain Barre syndrome
- Hepatitis
- Myasthenia gravis
- Pneumonitis
- Stevens Johnson Syndrome
- Toxic epidermal necrolysis
- Uveitis
- Iritis
- Myocarditis
- Any AEs that the Investigator considers to be of autoimmune or immune-related origin

Idera Pharmaceuticals, Inc.  
 Statistical Analysis Plan  
 Protocol Number: 2125-MEL-301

In addition, the Sponsor medical team also reviews all the events coded under 17 selected MedDRA SOCs that have the potential to identify irAEs (see the list of SOCs below). These AEs are reviewed relative to the dosing of either ipilimumab or tilsotolimod. They are also assessed in the context of the usage of concomitant medications and other AEs that occurred around the same time. This process allows for a holistic review of events in the context of other data elements, thereby providing an exhaustive process for potential irAE identification.

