**Table 2 List of MedDRA SOCs Used by Sponsor in Identification of Additional Potential irAEs**

MedDRA SOCs
Cardiac disorders
Endocrine disorders
Eye disorders
Gastrointestinal disorders
General disorders and administration site conditions
Hepatobiliary disorders
Immune system disorders
Injury, poisoning and procedural complications
Investigations
Musculoskeletal and connective tissue disorders
Neoplasms benign, malignant and unspecified (incl cysts and polyps)
Product issues
Renal and urinary disorders
Respiratory, thoracic and mediastinal disorders
Skin and subcutaneous tissue disorders
Surgical and medical procedures
Vascular disorders

The number and percentage of subjects who experienced at least one irAE will be tabulated. The preferred terms will be identified using the search strategy as described above. The frequency and percentage of immune-related TEAEs will be summarized by PT, as well as by PT and maximum grade. Similar analyses will be repeated for Grade 3 or above immune-related TEAEs and for Grade 3 or above treatment-related immune-related TEAEs. The frequency and percentage of treatment-related immune-related TEAEs will be summarized by PT and maximum grade.

Similarly, the frequency and percentage of immune-related serious TEAEs will be summarized by PT and maximum grade. Similar analysis will be repeated for Grade 3 or above immune-related serious TEAEs by PT. The number and percentage subjects who experienced immune-related TEAEs leading to permanent discontinuation of IMO-2125 and

Idera Pharmaceuticals, Inc.  
 Statistical Analysis Plan  
 Protocol Number: 2125-MEL-301

---

subjects who experienced immune-related TEAEs leading to permanent discontinuation of ipilimumab will be presented by PT.

A listing of immune-modulating medications which include thyroid hormone replacement therapies, systemic steroid and immuno-suppressants used after occurrence of irAE will be presented. Thyroid hormone replacement therapies will be identified by WHO drug ATC prefix H03, systemic steroids by WHO drug ATC prefix H02, and immuno-suppressants by WHO drug ATC prefix L04.

All irAEs will be listed. This listing will include treatment arm, age, sex, verbatim term and the corresponding coded terms, start date and study day, end date and study day, grade, serious (yes or no), relationship to treatment (yes or no), action taken, and outcome. It will also include an indicator for the source of the irAEs (CRF or sponsor-defined).

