14.1.7.2 Stratification Factor Levels from the Clinical Data, Intent to Treat Analysis Set	ORR, Final
14.1.8.1 Concomitant Medications, Safety Set	ORR, Final
14.1.8.2 Concomitant Medications for irAEs by Category, Safety Set	IDMC, ORR, Final
14.1.8.3 Cancer Treatments and Surgeries after Start of Study Treatment, Safety Set	ORR, Final
14.2.1.1.1 Summary of Independent Reviewer-Assessed Response by RECIST v1.1, Intent to Treat Analysis Set *	ORR, Final
14.2.1.1.2 Sensitivity Analysis: Summary of Objective Response Rate by RECIST v1.1, Full Analysis Set	ORR, Final
14.2.1.1.3 Sensitivity Analysis: Summary of Objective Response Rate by RECIST v1.1, Per Protocol Analysis Set	ORR, Final
14.2.1.1.4 Sensitivity Analysis: Un-Stratified and Best Case Scenario Analysis of Objective Response Rate by RECIST v1.1, Full Analysis Set	ORR, Final
14.2.1.2 Summary of Investigator-Assessed Response by RECIST v1.1, Intent to Treat Analysis Set *	ORR, Final
14.2.1.3.1 Concordance of Best Overall Response by Independent Reviewer and Investigator, Intent to Treat Analysis Set *	ORR, Final
14.2.1.3.2 Concordance of Objective Response Rate by Independent Reviewer and Investigator, Intent to Treat Analysis Set	ORR, Final
14.2.1.4.1 Subgroup Analysis: Summary of Objective Response Rate by RECIST v1.1 by Metastasis Stage, Intent to Treat Analysis Set	ORR, Final
14.2.1.4.2 Subgroup Analysis: Summary of Objective Response Rate by RECIST v1.1 by BRAF Mutation and Prior Targeted Therapy, Intent to Treat Analysis Set	ORR, Final

Idera Pharmaceuticals, Inc.  
 Statistical Analysis Plan  
 Protocol Number: 2125-MEL-301

Table Title	Timing of Analysis
14.2.1.4.3 Subgroup Analysis: Summary of Objective Response Rate by RECIST v1.1 by Duration of Prior Anti-PD-1 Therapy, Intent to Treat Analysis Set	ORR, Final
14.2.1.4.4 Subgroup Analysis: Summary of Objective Response Rate by Country, Intent to Treat Analysis Set	ORR, Final
14.2.1.4.5 Subgroup Analysis: Summary of Objective Response Rate by Baseline ECOG, Intent to Treat Analysis Set	ORR, Final
14.2.1.4.6 Subgroup Analysis: Summary of Objective Response Rate by Baseline LDH, Intent to Treat Analysis Set	ORR, Final
14.2.1.4.7 Subgroup Analysis: Summary of Objective Response Rate by RECIST v1.1 by Baseline Neutrophil/Lymphocyte Ratio, Intent to Treat Analysis Set	ORR, Final

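### The SAP's summaries of drugs used for immune-related AEs count only site-tagged drugs, while its irAE tables also count sponsor-defined irAEs, so irAE treatment may be understated relative to those tables

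*SAP*

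**What the plan says.** **Medications (SAP 9.5).** Two irAE-medication summaries are described, and both depend on the site's entry. The first covers drugs "used to treat immune-related adverse event as recorded on the Concomitant Medication eCRF page". The second groups drugs into three classes (ATC H03, H02 and L04) and includes "Any medications with one of these prefixes that were indicated on the Concomitant Medication eCRF page as being used to treat irAEs". The class summary is indexed in SAP 16.2 as "14.1.8.2 Concomitant Medications for irAEs by Category, Safety Set", for the IDMC, ORR and final outputs. The first summary is not separately indexed.

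**Events (SAP 11.5).** irAEs come from two sources. On the site side, "Any AEs which have been associated with the use of immunotherapy agents were marked as immune-related in the CRF". In addition, "the Sponsor medical team also reviews all the events coded under 17 selected MedDRA SOCs that have the potential to identify irAEs". That review looks at timing relative to dosing, and "They are also assessed in the context of the usage of concomitant medications and other AEs that occurred around the same time". For the irAE tables, "The preferred terms will be identified using the search strategy as described above", which covers both sources. The irAE listing flags each event as CRF or sponsor-defined, so the two groups remain distinguishable at analysis.

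**Protocol 10.1.3.4** counts as immune-related any event that the sponsor or the investigator considers so. It asks that irAEs be identified in the eCRF and that their treatment be recorded, including the AE being treated.

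**The concern.** The use of steroids, immunosuppressants or hormone replacement for irAEs is one of the main ways a reader judges how burdensome those events were. Table 14.1.8.2 will be read beside the irAE incidence tables; Table 14.3.2.6.1, for example, has the same IDMC, ORR and final timing. A reader will assume that both describe the same irAEs. They do not: the incidence tables include events added by the sponsor, while the treatment table depends on a tag set by the site. If the site did not regard an event as immune-related, it had no evident reason to tag the drug given for it. A steroid course could even form part of the context in which the sponsor classified an event as an irAE, and then be missing from the table of irAE treatment.

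**Working it through.** The plan states no figure to reproduce, so the check compares the two inclusion rules.

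**1. Define the sets for one drug class, at subject level.**
- *A*: subjects with a drug in the class that the site tagged as treating an irAE (SAP 9.5). This is what Table 14.1.8.2 counts.
- *B*: subjects with an untagged drug in the class given for a sponsor-defined irAE (SAP 11.5).
- The count that matches the irAE tables is |A ∪ B|.

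**2. Direction.** Shortfall = |A ∪ B| − |A| = |B \ A| ≥ 0. The mismatch can lower the table relative to the irAE tables and cannot raise it. This assumes that the sponsor's review only adds events, as SAP 11.5 describes (the heading of its SOC table refers to additional potential irAEs).

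**3. When the shortfall is zero.** It vanishes if every subject in *B* is already in *A* through another tagged drug. SAP 9.5 counts a subject once per term, so such a subject is already present. It also vanishes if sites updated their tags after the sponsor's review. Neither document provides for such an update.

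**4. Where drugs outside the tag appear.**

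| Output | Contains the drug? | By arm? | Attributed to an irAE? | Timing in SAP 16.2 |
|---|---|---|---|---|
| Table 14.1.8.2 | No | Yes | Yes | IDMC, ORR, Final |
| Table 14.1.8.1, all concomitant medications | Yes, if it meets the SAP 9.5 definition | Yes | No | ORR, Final |
| Listing 16.2.1.3.2, prior and concomitant medications | Yes | Subject level | Not as a count | ORR, Final |
| SAP 11.5 listing of the three classes used after an irAE | Yes; no tag restriction is stated | Subject level | By timing only | Not indexed |

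The last listing is described in the text of SAP 11.5 but is missing both from that section's closing list of outputs and from SAP 16.2.

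**5. Size.** |B \ A| needs the number of subjects with an untagged drug for a sponsor-defined irAE, and how many of them have no tagged drug in the same class. The documents give neither. For scale only: with 454 subjects randomised 1:1, an arm has 454 / 2 = 227 subjects, and each omitted subject is worth 100 / 227 = 0.44 percentage points if all are treated.

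**The case against.** The strongest case for leaving the plan alone has four parts.

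- **The rule is stated openly and is defensible.** In an open-label trial, the indication recorded by the site at the time may be preferred to a retrospective attribution by the sponsor. This stands as a reason to keep the tagged count. It does not justify placing it beside irAE tables built on a wider set with no matching row.
- **Few drugs may be affected.** Protocol 10.1.3.4 lists typical irAEs and has them treated as immune-related unless another cause is clearly established. The tag sits on the medication page, and subjects count once per term. This stands: a reader might infer that all treatment for sponsor-defined irAEs is lost, but the documents support only that untagged treatment is.
- **The drugs are not hidden.** Table 14.1.8.1 counts them by arm. This also stands; what is missing is their attribution to irAEs. SAP 16.2 does not mark that table for the IDMC, whereas it does mark Table 14.1.8.2.
- **The table is descriptive.** No safety hypothesis is tested (protocol 15.5), and the SAP does not define a proportion of irAEs requiring treatment. A misleading ratio arises only if a reader sets one table against the other. That is correct, but the shared subject and timing invite the comparison.

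Two further inferences are tempting and unsupported. One is that sponsor-added irAEs are disproportionately the treated ones. SAP 11.5 says only that medication use is part of the context, and that context may equally point to another cause. The other is that the shortfall differs by arm because attribution is open-label. That is possible, but nothing in the documents shows it.

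**Conclusion.** The mismatch is in the text of the SAP and its direction is certain under the stated rules: Table 14.1.8.2 may understate, and cannot overstate, treatment for the irAEs reported in the SAP 11.5 tables. The size is not derivable and could be zero; no percentage should be attached to it, and no difference by arm should be claimed. The conclusion rests on two assumptions: that the sponsor's review only adds irAEs, and that site tags are not revised afterwards. The retained sponsor-defined flag fits the second assumption but does not prove it. This is a consistency problem in a descriptive safety table that goes to the IDMC and both main reports. Type I error, power and the ORR and OS analyses are untouched.

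**What to change.** In SAP 9.5:

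1. Keep the eCRF-tagged count in Table 14.1.8.2 and label it as such.
2. Add an all-source row for each class: subjects with an H02, H03 or L04 drug whose recorded treated AE or indication belongs to the final SAP 11.5 irAE set, whether CRF or sponsor-defined. Handle the companion irAE-medication summary in the same way if it is produced.
3. Where a sponsor-defined irAE has no recorded drug link, either have the sponsor's medical team assign the link during its existing irAE review, or show drugs started on or after onset in a separate row labelled as date-based. Date matching should not feed the main count, because it also captures drugs given for other reasons; the eligibility criteria, for instance, allow limited steroid use in subjects with stable brain metastases.

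In SAP 16.2, add the listing of immune-modulating medications used after an irAE that SAP 11.5 already promises.

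The cost is SAP wording and some programming, plus a little medical-review time if links are assigned by hand. Treated proportions in the all-source row may be slightly higher than in the tagged row. Over-capture is confined to the date-based row, where the reader can see it.
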